We will enroll 20 facilities to participate in the cluster RCT. The intervention will involve working with and training HCWs at selected facilities and abstracting routinely collected programmatic data for HIV-infected children, adolescents and young adults aged 6-24 years attending the selected clinics (Table 3). We will also routinely abstract data from intervention tools being used at the facilities. We anticipate including up to 200 HCWs per intervention arm in the HCW training and intervention implementation and up to 2000 adolescents per arm. We will also enroll 400 adolescents and 200 HCWs to complete pre-trial surveys and 400 adolescents and 200 HCWs to complete post-trial surveys. HCWs from implementing sites will also participate in repeated surveys and planning meetings twice per month during the first 6 months of implementation of the ATP. We will conduct semi-structured interviews with up to 96 adolescents and 60 HCWs from all clinics included in the intervention arm of the trial. We will also complete FGDs with all HCWs from implementing facilities at 6 months into and at the end of the trial. At 6-monthly intervals, we will collect readiness assessment data from caregivers of children and adolescents who have not yet reached full disclosure, and adolescents and young adults ages 10-24 years who have attained full disclosure.

Program data abstraction: We will abstract program level data at baseline, and throughout the RCT to assess outcomes. Table 3 summarizes enrollment characteristics and data collection tools in the RCT arms.

Table 3: Details of cluster RCT design, enrollment and data collection

	Control arm	Intervention arm
Required Facility Characteristic	>300 clients in HIV care	>300 clients in HIV care
Estimated number of clients aged 6-24 per clinic	50-500	50-500
Minimum number of clients aged 6-24 per RCT arm	2000	2000
Procedures	Standard clinic procedures	Adolescent transition package
Disclosure checklist	√	√
Transition checklist	√	√
Process indicators	-	Disclosure milestones Transition milestones HCW, caregiver and client satisfaction
Maximum number of adolescents completing pre-trial surveys	200	200
Maximum number of HCWs completing pre-trial surveys		200
Maximum number of HCWs participating in repeated surveys and planning meetings		200
Maximum number of HCWs participating FGDs at 6 months		200
Maximum number of adolescents completing transition readiness assessment form	2000	2000

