	HCWs	Interviews with HCWs involved in pediatric/adolescent HIV care	38 (selected from clinics with different models of care)	
 ≥18 years of age -Provide clinical services to HIV-infected children and adolescents -Employed at facility in clinical care for at least 6 months and/or have a 1 year contract (i.e. not temporary staff)
	Policy maker and administrator heads	Policy makers at National and County level and HIV care partners or administrator head at facilities offering HIV care	30 interviews	
 ≥18 years of age -Employed by Ministry of Health at National or County level or a HIV care partner, at a level that involves policy making or in an administrative position at facilities offering HIV care
Aim 3: RCT				
Cluster RCT	Clinic clusters	Selected from clinics with >500 clients in care	20 clinics	
 ≥50 adolescents currently in HIV care -EMR data system -Facility leadership willing to take up intervention at their sites -Not actively already using transition or disclosure tools
Facility Survey Designee	HCW	Selected as representative for clinic to complete facility survey; will enroll 1-2 HCWs to help complete the survey per study site	20 clinics; surveys completed at baseline and study end	
 ≥18 years of age Employed at facility in clinical care for at least 6 months and/or have a 1 year contract (i.e. not temporary staff) Provides clinical services to adolescents
Pre-trial surveys	Adolescent	Selected from intervention and control sites	400 surveys	
 - Between 12 and 24 years of age -Willing to complete anonymous survey - Knows HIV status
	HCW	Selected from intervention sites	200 surveys	
 ≥18 years of age -Working in intervention clinics during the intervention -Providing adolescent HIV care
Intervention Implementation Monitoring	HCW	Selected from intervention sites	Repeated surveys every 2 weeks	
 ≥18 years of age -Working in intervention clinics during the first 6 months of intervention implementation -Providing adolescent HIV care
			Repeated planning sessions every 2 weeks	
 ≥18 years of age -Working in intervention clinics during the first 6 months of intervention implementation -Providing adolescent HIV care

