Based on previous data, we anticipate that we will be able to identify at least 50 adolescents per clinic for a total of at least 5000 adolescents. Assuming a prevalence of 60%, an intra-class coefficient (ICC) of 0.05 and a clinic size of 50 we would need to select 102 clinics for estimating the expected proportion with a 2.5% absolute precision and 95% confidence. With a sample size of 5,000 adolescents who are enrolled in HIV care during the previous 12-24 months, the precision of the estimates across possible ranges (50%-90%) of prevalence of retention in care or viral load suppression will range from $\pm 2.6\%$ to $\pm 1.5\%$ (Table 5). Thus, with 5000 adolescents or more, our study will have high precision in estimating the prevalence of retention in care and HIV viral load suppression, providing valuable input for understanding impact of interventions aimed at improving these adolescent HIV outcomes.

Table 7: Precision estimates for prevalence of retention and viral load suppression in HIV-infected adolescents

Indicator	Adolescents evaluated	Observed Prevalence	Events	CI	Precision
Retention or suppressed viral load	5000	50%	2500	47.4-52.6%	+/-2.6%
	5000	60%	3000	57.5-62.5%	+/-2.5%
	5000	70%	3500	67.6-72.4%	+/-2.4%
	5000	80%	4000	77.9-82.1%	+/-2.1%
	5000	90%	4500	88.5-91.5%	+/-1.5%

Aim 2: Given that the goal of the interviews conducted in this aim is to gather information on experiences with disclosure and transition and use this information to refine study tools, we believe that conducting 16 focus group discussions with adolescents (N=96), 16 focus group discussions with primary caregivers of adolescents (N=48), 38 interviews with HCWs and 30 interviews with administrators and policy makers, will give us adequate numbers to reach our study goal and enough diversity in experiences to ensure different perspectives are accurately represented in study tool refinement. A working group comprised of approximately 40 HCWs with significant expertise in providing care for HIV-infected children, adolescents and adults will be

sufficient to foster rich discussions around study tools. Including approximately 40 HCWs, will allow participation of all stakeholders.

Aim 3: For the RCT, using a conservative estimate of 20% of clients being between 10-24 years old and each clinic having at least 500 active clients, we anticipate 200 eligible clients per clinic, for a total of 1000 eligible clients per randomization arm.

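### Tables 3 and 4 give different clinic-size thresholds, no stated rule secures the 2000 clients per arm, and Table 8's cluster size is twice or more what those rules imply

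*Combined protocol and SAP*

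**What the plan says.** **Clinic size.** Table 3 (cluster RCT design) gives the facility requirement in both arms as ">300 clients in HIV care". Table 4, in the sampling column of the Aim 3 row, has "Selected from clinics with >500 clients in care". Section 11a plans for Aim 3 "using a conservative estimate of 20% of clients being between 10-24 years old and each clinic having at least 500 active clients".

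**Adolescents per clinic.** The only head-count among Table 4's inclusion criteria for trial clinics is "≥50 adolescents currently in HIV care". Table 3 has a row "Estimated number of clients aged 6-24 per clinic", filled in as 50 to 500.

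**Clients per arm.** Table 3's row "Minimum number of clients aged 6-24 per RCT arm" shows 2000 in each arm. The Aim 3 text of Section 5b has "up to 2000 adolescents per arm", and the records-review row of Table 4 likewise treats 2000 per arm as an upper limit. Section 11a arrives at 200 eligible clients per clinic and 1000 per arm.

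**Power.** Table 8 sets 100 clients per clinic in each of two age bands (10-15 and 16-24). That is 200 per clinic and, with ten clinics, 2000 per arm. The accompanying text gives alpha 0.05, 80% power and a between-clinic coefficient of variation of 0.3.

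**The concern.** A site list can satisfy the written criteria and still supply far fewer clients per clinic than Table 8 uses. Which threshold applies matters, because the protocol's own 20% share turns 300 clients into 60 and 500 into 100, against the 200 that Table 8 needs. The figure of 2000 gives no protection: it appears as a minimum in one place and a maximum in others, and no entry rule delivers it.

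At stake is whether ten clinics per arm are enough for the disclosure, transition and loss-to-follow-up comparisons that Table 8 is meant to justify.

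**Working it through.** **Step 1. Clients per arm under each rule (10 clinics per arm).**

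- Floor of 50 adolescents: 10 × 50 = 500.
- Table 3 threshold: 20% × 300 = 60 per clinic; × 10 = 600.
- Table 4 and Section 11a threshold: 20% × 500 = 100 per clinic; × 10 = 1000.
- Needed for 2000 per arm: 2000 / 10 = 200 per clinic, which is 40% of a 500-client clinic (200/500) or 67% of a 300-client clinic (200/300).

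The 20% covers ages 10-24, whereas Table 3's 2000 covers ages 6-24. The share aged 6-9 is not given, so the 600 and 1000 are somewhat low as counts for ages 6-24. They would have to more than triple, or double, to reach 2000.

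**Step 2. Section 11a's own arithmetic.** 20% of 500 is 100 per clinic, not the 200 stated. Ten clinics at 200 give 2000 per arm, not the 1000 stated.

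**Step 3. Reproduce Table 8.** The formula is the Hayes-Bennett one for unmatched clusters. Alpha is taken as two-sided, since the protocol does not say.

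V = p0(1−p0)/m + p1(1−p1)/m + k²(p0² + p1²)

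c = 1 + (1.96 + 0.84)² × V / (p0 − p1)², rounded up, with k = 0.3 and m = 100 per band

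Example, effective transition 10% vs 20%: V = 0.0009 + 0.0016 + 0.09 × 0.05 = 0.0070. Then c = 1 + 7.85 × 0.0070/0.01 = 6.49, so 7, as stated.

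All 11 rows that give two proportions and a clinic count match:

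| Row | Computed | Table 8 |
|---|---|---|
| Disclosure started, 50% vs 80 / 90 / 100% | 8.34 / 5.85 / 4.61 | 9 / 6 / 5 |
| Disclosure complete, 30% vs 50 / 70% | 7.91 / 3.77 | 8 / 4 |
| LTFU 20% vs 10% | 6.49 | 7 |
| Transition discussed, 20% vs 40%, 20% vs 60%, 50% vs 100% | 5.32 / 2.96 / 4.61 | 6 / 3 / 5 |
| Transition complete, 10% vs 20% | 6.49 | 7 |
| LTFU 25% vs 15% | 9.48 | 10 |

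The match fails at 50 or 60 per band, with k = 0.2 or 0.25, or without the added 1.

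**Step 4. Same formula at the cluster sizes the rules imply.** Clients are assumed to split evenly between the two bands. Power with c = 10 is Φ(√[(c − 1)(p0 − p1)²/V] − 1.96). Cells show clinics needed per arm, then power with ten.

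| Row | 100 per band (Table 8) | 50 per band (500 clients) | 30 per band (300 clients) | 25 per band (floor of 50) |
|---|---|---|---|---|
| Disclosure 30–50% | 8; 89% | 9; 85% | 11 (10.01 rounded up); 79.9% | 11; 77% |
| Transition 10–20% | 7; 95% | 9; 87% | 12; 75% | 13; 70% |
| LTFU 20–10% | 7; 95% | 9; 87% | 12; 75% | 13; 70% |
| LTFU 25–15% | 10; 82% | 12; 72% | 16; 61% | 17; 56% |

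Example, transition at 30 per band: V = 0.25/30 + 0.0045 = 0.01283, so c = 1 + 7.85 × 1.283 = 11.07, giving 12.

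The other seven rows need ten clinics or fewer throughout. Even at 25 per band they need 10, 7 and 5 (disclosure started), 5 (disclosure 30–70%) and 8, 4 and 5 (transition discussed).

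**The case against.** The strongest reply has four parts.

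1. **The thresholds are compatible.** A clinic above 500 is also above 300, and two of the three places that give a size use 500. This stands: a reader might infer that the two rules exclude each other, but they do not. What is missing is a statement of which one governs. If it is 500, the two headline outcomes keep more than 80% power.

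2. **A per-clinic floor is not meant to guarantee an arm total.** Table 3 expects 50 to 500 clients per clinic, a mean of 200 lies inside that range, and Section 7c says clinics are chosen partly on size. This also stands. It would be wrong to conclude that the arms will contain 500 or 600 clients, because the documents do not say how large the chosen clinics are. But a figure labelled as a minimum should follow from some rule, and this one does not.

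3. **Most of Table 8 is robust.** True: seven of the 11 rows survive even the lowest case. A reader might infer that missing Table 8's cluster size leaves every comparison underpowered, and the arithmetic does not support that.

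4. **The SAP has moved on.** Its primary endpoint is transition readiness at ages 15-24, with its own power table at an average cluster size of 50. So this point does not show that the SAP's primary analysis is underpowered. Table 8 remains the protocol's justification for disclosure, transition and loss to follow-up. The 50-adolescent rule is not limited to ages 15-24, so it does not secure the SAP's cluster size either.

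**Conclusion.** The inconsistency is established from the text: two unreconciled thresholds, 2000 per arm used both as a floor and as a cap, and two arithmetic slips in Section 11a. Table 8 rests on 200 clients per clinic, while a clinic that just meets the stated rules would be expected to supply 50 to 100.

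The consequence is moderate and conditional. If 500 governs, one row of 11 drops below 80% power. If 300 governs, or clinics sit at the floor of 50, four rows do, although disclosure 30–50% at 300 clients misses by a fraction of a point.

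These results assume an even split between age bands, the protocol's 20% share, two-sided alpha, equal cluster sizes, and every clinic at the threshold in question. Larger clinics would reduce or remove the loss. The figures also take Table 8's denominators as given. Section 11a expects only 20 of the 100 older clients per clinic to be eligible to transition, which is a separate question and is not counted here.

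**What to change.** - State one clinic-volume criterion and use it in Table 3, Table 4 and Section 11a.
- Correct Section 11a so that the share, the count per clinic (100 or 200) and the count per arm (1000 or 2000) agree, with one age range throughout.
- Relabel 2000 per arm as an expected or maximum number, consistently in Table 3, Section 5b and Table 4, or replace it with the figure the criterion supports.
- Recompute Table 8 at the resulting cluster size in each age band, and state the assumed age split.

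If the chosen clinics are known to be larger than the thresholds, giving their actual counts by age band would serve equally well. The cost is table edits and somewhat less favourable stated power, mainly for loss to follow-up at ages 16-24 if 500 is the criterion. No extra clinics or participants are needed to make the correction.

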We will conduct a cluster RCT to evaluate a combined disclosure intervention and adapted transition tool (ATP) to increase disclosure among young adolescents and improve effective transition to adult care for pediatric patients. Cluster RCTs are well-suited to interventions that occur at the clinic, rather than individual level. The randomization at a clinic level allows for the traditional benefits of randomization. We will include a total of 20 clinics in the RCT, 10 receiving standard of care and 10 receiving the intervention and compare disclosure and transition outcomes between the 2 arms. We will periodically abstract routinely collected medical record information to determine proportions of adolescents with full disclosure and transitioned to adult care in addition to routinely extracting data from study data collection tools. We will conduct pre-study baseline surveys with adolescents and HCWs. We will also monitor initial implementation using modified plan-do-study-act cycles and surveys and FGDs with implementing HCWs. At the end of the study, we will conduct qualitative interviews and focus groups with adolescents and HCWs in the intervention sites, including 10 study nurses implementing trial procedures, and post-study surveys with adolescents and HCW to assess acceptability, appropriateness, feasibility, and intervention fidelity of the tools. Throughout the study, at 6-monthly intervals, we will collect readiness assessment data from caregivers of children and young adolescents preparing for disclosure, and adolescents and young adults ages 10-24 who have attained full disclosure.

SECTION 5: STUDY SITES AND POPULATIONS

5a. Study sites

Aim 1: We will perform facility surveys and abstract routinely collected programmatic data at 102 clinics in Kenya utilizing EMR systems. Clinics will be randomly selected from among clinics with EMR.

Aim 2: We will recruit HCWs from clinics throughout Kenya for the working group meeting. We will select caregivers of HIV-infected adolescents, HIV-infected adolescents, and HCWs from KNH and 6-10 facilities participating in AIM 1 for individual interviews and focus groups. We will

invite policy makers from national and county level institutions and hospital administrators from facilities participating in Aim 1.

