The transition intervention will be delivered either in person or on phone by clinic based health care workers where possible, or by phone by hired study staff. Delivery will be guided by current recommendations and guidelines from the Kenyan MOH regarding care for adolescents living with HIV and country mandates.

Transition readiness assessments will be conducted through phone interview rather than in person. These were already conducted by study staff, and will continue to be conducted by the same hired study staff.

Enrolled participants will give oral consent by phone (using the phone interview guide) to continue with transition readiness assessments by phone. This will be obtained and documented by study staff. Study link logs will be converted to electronic logs with password protection and accessible only to study staff to limit visits to the clinic by study staff.

Enrolled participants in intervention and control sites will receive phone calls from study staff to see how they are coping, adhering to treatment and receive COVID-19 related information.

Participants will be reimbursed via mobile money transfer for the 6 monthly transition readiness assessments.

All new enrollment is suspended, but may be reopened when identified as safe and clinical procedures for adolescents living with HIV are returned to normal in the country.

In-person disclosure related study activities are suspended; however, HCWs in facilities can use disclosure tools as needed to assist them with providing routine care for adolescents living with HIV and their primary caregivers.

In-person continuous quality improvements (CQI) activities are suspended, phone based or other virtual CQI activities may resume if possible and may include multiple shorter check-in phone visits with individual, rather than groups, of healthcare providers, and will check in on healthcare providers well-being including how they are coping with COVID-19.

FGDs scheduled to be held with HCWs after 6 months of intervention implementation will be postponed until it is deemed safe to meet in person or virtual delivery/hosting platforms have been identified and organized.

When determined to be safe, and in accordance with MOH and country-specific guidelines, study procedures will return to those detailed below that involve in-person interactions.

Overview:

Study procedures consist of:

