To track intervention effectiveness for improving adolescent outcomes, we will also abstract data from EMR systems and paper forms in both intervention and control sites (adolescent checklist and other paper based forms) at baseline (before RCT start), and throughout the duration of the RCT. We will work with data personnel in each of the facilities to develop operating procedures on data abstraction, making use of currently used systems and procedures for reporting data that are already in place at that clinic. All data handled by the study team will be handled and stored as described in aim 1 procedures.

Transition readiness surveys and disclosure readiness surveys will be collected either on paper CRFs or using REDCap on Tablets. This survey will be administered by a trained clinic staff member or hired study staff. The readiness assessment survey tools are provided as an appendix. Data collected on paper forms will be entered into REDCap by study staff.

List of procedures for the RCT

- a. Meeting with clinic team and leadership to present study and study team
- b. Select 20 clinics for randomization
- c. Conduct baseline pre-trial surveys with adolescents and HCWs
- d. Training of clinic staff on the use of the ATP (intervention sites only)
- e. Training on data collection tools for all sites (disclosure and transition checklists)
- f. Share baseline data with clinic if available
- g. Pre-trial surveys with HCWs on implementation climate
- h. 6 month intensive clinic support and optimization of ATP implementation
- i. Twice-monthly surveys with HCWs and meetings facilitated by the study team aimed at making adaptations and changes to the tool as needed
- j. Completion of study adaptation log and PDSA worksheet

- k. Completion of baseline and 6-monthly transition readiness surveys with adolescents ages 15-24
- l. Completion of baseline and 6-monthly disclosure readiness surveys with caregivers of adolescents ages 6-17 who do not know their HIV status
- m. Extraction of routine medical records for adolescents ages 6-24
- n. Extraction of data from intervention tracking forms
- o. Continuous support as needed for implementation

7d. Implementation Evaluation

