Adolescent interview questions will focus on personal experiences with HIV disclosure and/or transition and seeking and receiving HIV treatment and care services. For HCWs, discussion questions will focus on the services offered to adolescents at their facility and personal experiences with use of the transition and disclosure tools. Similar to the FGD discussion guides, IDI guides for HCWs will include questions to assess implementation context based on the constructs and domains from CFIR. ATTACH study nurse IDIs will include questions to evaluate delivery of the transition readiness assessment, a tool only administered by study staff. IDIs will be conducted by a trained interviewer using a semi-structured flexible interview guide and will take approximately 60 minutes to complete. IDIs will be conducted in Kiswahili, Luo, English or other language appropriate for the location where activities are taking place. With consent from participants, discussions will be audio-recorded. At the beginning of the interview, interviewers will describe the goal of the interview and information about participation, including the ability to skip questions and the confidentiality of information shared.

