Recruitment Scripts:

Study Activity	Recruitment Script
Aim 1`	
Facility Survey	Facility Survey Recruitment Script
Aim 2	
Adolescents in HIV care (48 not completed transition, 48 transitioned)	NA
	Caregiver recruitment script for adolescent IDI and FGD
	Adolescent recruitment script
Caregivers	Caregiver recruitment script
Policy makers	Policy maker/Admin/HCW recruitment script
HCW/Administrator	Policy maker/Admin/HCW recruitment script
Working group	HCW recruitment script for Workshop
Aim 3	
Pre-Trial surveys	Adolescent Recruitment Script*
Implementation Activities	HCW IS Activities Recruitment Script
Post-trial IDI	NA
	Adolescent recruitment script*
	Caregiver recruitment script*
	HCW recruitment script*
Implementation FGDs	HCW FGD Recruitment Script
Transition readiness	Adolescent recruitment script*
Disclosure readiness	Caregiver recruitment script
Post-trial surveys	Adolescent recruitment script*
	HCW recruitment script*

*Same as aim 2 document

ATTACH STUDY ANALYSIS PLAN (Finalized 2.13.2020)

SUMMARY

Study Purpose: To determine whether an adolescent transition package (with transition and disclosure tools) improves **mean transition readiness** among HIV positive adolescents in care in Kenya.

Study Design: Cluster randomized trial

Study Population and Sites:

Population:

- HIV-positive adolescents and youth between the ages of 10 and 24

Sites:

- 20 HIV clinics in Nairobi, Nakuru, Homabay and Kajiado, Kenya

Study Duration: Estimated 18 months total (enrollment and 1-year follow-up)

Randomization: 10 clinics randomized to intervention sites and 10 to control.

Intervention:

Adolescent Transition Package (ATP): The ATP will consist of a validated disclosure booklet and disclosure tracking tool, and a HCW administered transition booklet and transition tracking logs, implemented in intervention sites. HCW in intervention sites will be trained on implementation of the ATP with continued support for the clinic in the first 3 months of the intervention. In control sites, parallel data collection for primary outcomes will be conducted.

Primary endpoints: Transition readiness

Secondary endpoints: Overall clinic retention and overall viral suppression

Exploratory outcome: % with full disclosure, Time to full disclosure, Post transition retention

DATA ANALYSIS

Primary outcome: transition readiness among HIV positive adolescents age 15-24

- a. Transition readiness score overall (all domains)
- b. Treatment literacy readiness score

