- c. Self-management readiness score
- d. Communication readiness score
- e. Support readiness score

Analysis

Primary analysis ITT: Mixed effects linear regression to compare transition readiness scores (overall and by domain) over time in control and intervention sites with adjustment for multiple testing (Benjamin-Hochberg method).

Time points: Enrollment, month 6, month 12

Sample size and power table

Assumptions: 80% power, alpha 0.05, ICC 0.2, average cluster size of 50

Mean difference	SD	Number of Clusters per Arm
0.5	1	4
0.5	2	15
1.0	2	4
1.0	3	9
1.5	3	4
1.5	4	7
2.0	5	6
2.0	6	9

Secondary outcomes

- a. Overall retention in 10-24 year olds: defined as proportion of 10-24 year olds completing visits within 6 months of last visit
- b. Overall viral suppression: defined as proportion of 10-24 year olds with viral load of less than 1000 copies per ml after at least 6 months of ART

Analysis

Overall retention/suppression: Generalized estimating equations (GEE) to compare retention and viral suppression in intervention and control sites

Time-points: Baseline, month 6, month 12

Minimum detectable differences in proportions with outcomes

Assumption: 80% power, alpha 0.05, ICC 0.2, 10 clusters per arm, average cluster size of 50

Proportion with outcome in arm 1	Proportion with outcome in arm 2
0.2	0.31
0.3	0.44
0.4	0.56

0.5	0.69
0.6	0.81
0.7	0.93

Exploratory analyses

1. Post-transition retention defined as completing and adult clinic visit day after transfer to adult services and at least 1 other visit within 6 months of the adult visit (total of 2 visits):
Analysis: GEE to compare post-transition retention in intervention and control sites
2. Principal components analysis to identify the most representative components of data in the 4 domains of the readiness assessment checklist (HIV treatment literacy (Q 1-5), self-management (Q6, 7, 9-14, communication Q16-19, support 20-22) and then factor analysis to determine the most important components.
3. Proportion of children with full disclosure and time to full disclosure. Children who do not know their HIV status from HCW assessment. Child will be asked why they are taking medicine; if they report they have HIV they have reached full disclosure. If they mention any other illness or other responses they will not have reached full disclosure.
End point: Child says they have HIV in response to the question “why are you taking your medicine”
Analysis: Descriptive %, time to full disclosure

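### Nothing in the plan stops study staff who deliver the transition intervention by phone from also scoring the primary readiness outcome for the same adolescents in this unmasked trial

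*Combined protocol and SAP*

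**What the plan says.** The SAP (Data Analysis) defines "Primary outcome: transition readiness among HIV positive adolescents age 15-24", as an overall score and four domain scores: treatment literacy, self-management, communication and support. It lists "Time points: Enrollment, month 6, month 12" and a mixed effects linear regression under ITT.

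Protocol Section 7 (COVID-19 adapted study procedures) has the transition intervention delivered in person or by phone "by clinic based health care workers where possible, or by phone by hired study staff". The following paragraph moves the readiness assessments to phone interview and adds: "These were already conducted by study staff, and will continue to be conducted by the same hired study staff".

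On who may administer the readiness tool, the protocol is not consistent:

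- Section 7c (Data collection procedures), directly after a sentence naming both the transition and the disclosure readiness surveys: "This survey will be administered by a trained clinic staff member or hired study staff".
- Section 7d (Qualitative Interviews), of the transition readiness assessment: "a tool only administered by study staff".
- Section 10 (Data Capture and Storage Methods): study staff carry out the transition readiness surveys.

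Section 5f rules out masking, and Section 7c repeats that the study is not blinded. The Appendices list two separate pandemic scripts, one for the readiness assessment and one for the transition intervention.

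**The concern.** Readiness is measured by interview, and Section 10 says the survey covers medical knowledge and skills in being independent. If the interviewer is the person who taught the adolescent that material, the interviewer may prompt or credit doubtful answers, and the adolescent may say what that person hopes to hear. Control participants receive no ATP content, so this particular conflict can arise in the intervention arm only. It would enter at month 6 and month 12, after delivery has begun, and so would look like a greater gain in readiness under the ATP. The plan has no rule separating delivery from assessment, and the SAP has no sensitivity analysis for it.

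**Working it through.** **1. Can the roles overlap?** Read together, the texts give:

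| Question | Section 7 (COVID-19) | Section 7c | Sections 7d and 10 |
|---|---|---|---|
| Who delivers? | Clinic HCWs where possible, otherwise study staff by phone | Intervention-site staff are trained in the tools | – |
| Who assesses transition readiness? | Study staff, by phone | Clinic or study staff | Study staff |
| Are the roles kept apart? | Not stated | Not stated | Not stated |

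Section 4 (Aim 3) places among the intervention-site interviewees HCWs "including 10 study nurses implementing trial procedures". There are 10 intervention clinics, and Section 7d asks the study nurses about giving the readiness assessment. So some assessors work at intervention sites, and Section 7 lets study staff deliver. Overlap is possible; no text says that it happens.

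**2. Does the analysis remove it?** Let b be the arm-average shift: the share of intervention assessments scored by the deliverer times the mean shift in those assessments. The arm contrast at month 6 or 12 then estimates the ATP effect plus b. ITT fixes who is analysed, the mixed model handles clustering and repeated measures, and the Benjamini-Hochberg step handles five related tests. None of these subtracts b. Adjusting for enrollment scores does not either, because b arises after enrollment.

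**3. The SAP power table.** Inputs: 80% power, alpha 0.05 (two-sided assumed), cluster size 50, printed ICC 0.2. Clusters per arm = 2 × (SD × 2.8016 / difference)² × (1 + 49 × ICC) / 50, rounded up. For the row with difference 1.0 and SD 3:

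- ICC 0.2: 2 × 9 × 7.849 × 10.8 / 50 = 30.5, so 31; the SAP prints 9.
- ICC 0.04: 2 × 9 × 7.849 × 2.96 / 50 = 8.36, so 9.

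Over all eight rows the printed ICC gives 14, 55, 14, 31, 14, 25, 22, 31 against the SAP's 4, 15, 4, 9, 4, 7, 6, 9. ICC 0.04 gives the SAP's figures exactly. That mismatch is a separate matter; here both values are carried.

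**4. What would a given b do?** With 10 clusters of 50 per arm, the SE of the arm difference in SD units is √[2 × (1 + 49 × ICC) / 500]. This is 0.208 at ICC 0.2 and 0.109 at ICC 0.04. With a t test on 18 df the significance thresholds are 0.437 SD and 0.229 SD. The probability of a significant result with no true effect (noncentral t, two-sided 5%) is:

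| Assumed b (SD) | ICC 0.2 | ICC 0.04 |
|---|---|---|
| 0 | 0.050 | 0.050 |
| 0.1 | 0.074 | 0.140 |
| 0.2 | 0.149 | 0.413 |
| 0.25 | 0.207 | 0.585 |
| 0.33 | 0.330 | 0.826 |

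This is one cross-sectional comparison. It ignores enrollment scores, repeated measures and the multiplicity adjustment.

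**5. What might b be?** The SAP (Exploratory analyses, item 2) assigns 5 + 8 + 4 + 3 = 20 questions to domains. If each is scored 0/1 (assumption), one extra favourable answer is 1.0 point. The SAP's SDs run from 1 to 6, so that is anything from 1.00 to 0.17 SD if every intervention assessment were affected. If 30% were affected (assumption), the mean shift is 0.3 points, or 0.30 to 0.05 SD. The range is too wide to support any one figure.

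**The case against.** The overlap is an inference. A reader might take Section 7 to say that the phone deliverers and the assessors are the same people. Read naturally, "These were already conducted by study staff, and will continue to be conducted by the same hired study staff" refers to those who did the assessments before the pandemic, and study-staff delivery is a fallback for a period after which procedures are to revert. This stands: the text permits the overlap and does not assert it.

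A reader might also infer from Section 7c that ATP-trained clinic staff score the primary outcome. Section 7 (COVID-19), Section 7d and Section 10 all give the transition readiness assessment to study staff, and the clinic-staff wording in 7c may have been meant for the disclosure survey. That strand is a wording conflict to be reconciled.

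The assessment has its own call script, separate from the intervention script, which may limit prompting. The script, items and scoring are not shown, so neither leniency nor its absence can be established. It is likewise unknown whether the forms already capture the assessor's identity.

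Nor do the documents support saying that the bias always favours the ATP: someone who knows the adolescent could score more strictly, and giving the correct taught answer is partly the learning that the outcome should capture. Both arms also receive study-staff calls about coping and adherence. Those calls balance general contact but not the teaching of assessed content, so they do not answer the point.

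**Conclusion.** The point holds as a gap in the plan. In an unmasked trial, Section 7 permits the person who delivered ATP content by phone to score the primary outcome for the same adolescent, and nothing forbids it. Any resulting bias would be specific to the intervention arm, would most likely favour the ATP, and would not be removed by ITT or the mixed model.

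Its size is unknown. It is tempting to conclude that one lenient answer per interview equals a whole target effect, since the SAP table lists differences of 0.5 to 2.0 points. That does not follow: it assumes 0/1 scoring and overlap in every intervention interview, ignores the table's SDs of 1 to 6, and treats a grid of scenarios as a single target. The table's standardised differences are 0.25 to 0.5 SD. An arm-average bias of 0.2 SD would give significance with probability 0.15 to 0.41 across the two ICC values, but 0.2 SD is an assumption. The gap does not show the trial to be biased; it warrants a cheap improvement that protects the primary endpoint.

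**What to change.** 1. In Section 7 (COVID-19) and Section 7c, state that no one who delivered ATP content to an adolescent conducts that adolescent's month 6 or month 12 readiness assessment. Because Section 6 lists a readiness assessment among the ATP tools, say that giving this assessment does not itself count as delivery.
2. While assessments are by phone, swap these calls among existing study staff across clinics, using the assessment script and without showing arm on the call list where feasible.
3. Record assessor ID, deliverer ID and delivery mode, if the forms do not already do so.
4. Add to the SAP a supportive sensitivity analysis that keeps all randomised participants and examines or adjusts for deliverer-scored assessments, labelled as a non-randomised comparison. Do not rely on excluding them: that would drop post-randomisation data from one arm only, and selectively where clinic HCWs could not deliver.
5. Reword Section 7c so that only study staff administer the transition readiness survey, in line with Section 7 (COVID-19), Section 7d and Section 10. Leave the disclosure readiness survey unchanged.

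The cost is a reassignment of calls and a few form fields, with no added staff. The drawbacks are language matching, controlled sharing of the already electronic, password-protected link logs, and care over inadvertent disclosure of HIV status when an unfamiliar caller phones, a risk that Section 12 already raises for phone activities. Masking will be imperfect, since adolescents may reveal their arm during the call.
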